 - N/A. Use of the dexamethasone pellet and immunosuppressive drug therapy are each part of standard clinical care in the treatment of active intermediate and posterior uveitis. The dexamethasone pellet is FDA-approved for the treatment of intermediate and posterior uveitis.
- e. Justification for inclusion of a placebo or non-treatment group.
 - N/A. There is no placebo or non-treatment arm in this pilot study.
- f. Definition of treatment failure or participant removal criteria.
 - N/A
- g. Description of what happens to participants receiving therapy when study ends or if a participant's participation in the study ends prematurely.

- Since all treatments are currently used in the clinical care of uveitis patients, all patients enrolled in this study will be able to continue receiving therapy according to best medical judgment once the study ends.

5. Inclusion/Exclusion Criteria Inclusion Criteria:

- Active sight-threatening intermediate or posterior uveitis for which immunosuppressive drug therapy is planned and the physician is considering treatment with high-dose corticosteroid to control the uveitis whilst immunosuppressive drugs are being instituted or adjusted.
 - o Note: it is acceptable for the patient to already be on an immunosuppressive drug as long as high dose corticosteroids are indicated.
- Patients must be age 18 years or older (the dexamethasone pellet is not FDA-approved for pediatric use) and sign an informed consent.
- The ocular media must be clear enough to obtain OCT and fundus photographs.
- No elective intraocular surgery should be planned for the first 3 months after enrollment.

Exclusion Criteria:

- Infectious uveitis
- History of scleritis
- Active or suspected viral infection of the cornea or conjunctiva
- History of mycobacterial or fungal disease
- HIV positivity
- Age <18 years old
- Allergy to dexamethasone
- Uncontrolled IOP
- Advanced glaucoma
- Aphakia with rupture of the posterior lens capsule
- ACIOL with rupture of the posterior lens capsule
- Media opacity that would preclude evaluation of the posterior pole via fundus photography or OCT assessment
- Planned elective ocular surgery within 3 months of enrollment Any systemic disease requiring systemic corticosteroids.

6. Drugs/ Substances/ Devices

a. The rationale for choosing the drug and dose or for choosing the device to be used.

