 - The cumulative incidence of control of inflammation (0.5+ or less vitreous cells in the liquid vitreous; trace or less anterior chamber cells; and inactive chorioretinal lesions) at the 3month visit and the 6-month visit will be compared to the published data (from Johns Hopkins and from the SITE database) of the cumulative incidence of steroid-sparing success (prednisone <=7.5 mg daily and controlled disease) and of oral steroid discontinuation with the goal of proving NON-INFERIORITY of the dexamethasone pellet. Cumulative incidences of ocular and systemic side effects of the dexamethasone pellet will be compared to those of oral prednisone via rates and cumulative incidences at 12 months.
- c. Statistical plan including sample size justification and interim data analysis.
 - 20 patients will be enrolled and the data regarding success of control of uveitis at the 6 and 12 month examinations will be compared with historical published data. Comparative data from the Johns Hopkins cohort, SITE database, and published MUST data will be utilized. d. Early stopping rules.
- None

8. Risks

- a. Medical risks, listing all procedures, their major and minor risks and expected frequency.
 - Dexamethasone pellet insertion within 14 days of the baseline visit and potential insertion at months 3, 6, 9, and every 3 months thereafter based on the study protocol and clinical judgment of the PI/study ophthalmologist.
 - Dexamethasone pellet should not be used if patient is allergic to any of its ingredients.
 - Injections into the vitreous in the eye may be associated with eye inflammation, subconjunctival hemorrhage, and transient increased eye pressure. Rarely, intravitreal injections may be associated with vitreous hemorrhage, retinal detachment, or endophthalmitis. The risk of performing an intravitreal injection as part of this study is no greater than that associated with clinical care in the treatment of uveitis. The study ophthalmologist will monitor the patient regularly after each injection.

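### The historical comparators are not restricted to patients who meet the trial's own eligibility criteria, so the non-inferiority comparison in 7b can be biased, in a direction the documents do not settle

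*Combined protocol and SAP*

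**What the plan says.** Section 5 defines a selected population. The main inclusion criterion is "Active sight-threatening intermediate or posterior uveitis for which immunosuppressive drug therapy is planned", with high-dose corticosteroid under consideration. A note adds that "it is acceptable for the patient to already be on an immunosuppressive drug as long as high dose corticosteroids are indicated". The last exclusion is "Any systemic disease requiring systemic corticosteroids"; it names no dose. Uncontrolled IOP and advanced glaucoma are also excluded, without thresholds.

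Section 4e confirms that there is no placebo or untreated arm. Section 7a compares control of uveitis with historical data from Johns Hopkins and SITE. Section 7b sets the non-inferiority goal at 3 and 6 months. The pellet side is "The cumulative incidence of control of inflammation (0.5+ or less vitreous cells in the liquid vitreous; trace or less anterior chamber cells", together with inactive chorioretinal lesions. The historical side is the "cumulative incidence of steroid-sparing success (prednisone <=7.5 mg daily and controlled disease) and of oral steroid discontinuation", taken from published Johns Hopkins and SITE data. Section 7c says "Comparative data from the Johns Hopkins cohort, SITE database, and published MUST data will be utilized".

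None of these sections says which historical patients count, or that the data will be matched, weighted or adjusted. None gives a historical rate, a margin or an alpha.

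**The concern.** With no concurrent control, a difference between the trial and the historical rate mixes the effect of the pellet with any difference between the two populations. Section 5 shapes one population, and nothing in section 7 shapes the other.

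One exclusion makes this specific. The 7b benchmark contains a systemic steroid dose. A historical patient kept above 7.5 mg for a systemic disease fails steroid-sparing success even with quiet eyes, and one kept on any oral dose fails discontinuation. The trial enrols no patient with such a disease. If the comparator contains them, they pull the benchmark down and make non-inferiority easier to claim. The effect comes only from their presence in the comparator: the pellet side carries no dose condition, so the exclusion removes no failures from the trial arm.

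At stake is whether a non-inferiority statement from 20 patients would mean what it says.

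**Working it through.** The plan gives no rate, margin, alpha or power behind its 20 patients, so there is no figure to reproduce. The check shows how much an unrestricted comparator could matter.

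**Inputs**
- n = 20, single arm (7c).
- p = 0.60, success in historical patients who would meet section 5 (assumed).
- q = share of historical patients with steroid-requiring systemic disease: 0, 0.10, 0.20, 0.30 (assumed).
- k = their success relative to p: 0 if all fail, 0.5 if they succeed half as often (assumed).
- Margin 0.15 and one-sided alpha 0.025 (assumed). The historical rate is treated as fixed and known.

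**Benchmark**

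Unrestricted rate = p(1 − q) + k·p·q.

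With k = 0: 0.60 × 1.00 = 0.60; 0.60 × 0.90 = 0.54; 0.60 × 0.80 = 0.48; 0.60 × 0.70 = 0.42. The benchmark falls by 0, 6, 12 or 18 points.

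**Effect on the claim**

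Non-inferiority is declared if at least c of 20 succeed, where c is the smallest count with exact binomial P(X ≥ c | benchmark − 0.15) ≤ 0.025. The false-claim chance is P(X ≥ c) when the pellet is truly worse than comparable patients by the full margin, that is, at 0.60 − 0.15 = 0.45.

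| q (k = 0) | Benchmark | Benchmark − 0.15 | c | False-claim chance |
|---|---|---|---|---|
| 0 | 0.60 | 0.45 | 14 | 2.1% |
| 0.10 | 0.54 | 0.39 | 13 | 5.8% |
| 0.20 | 0.48 | 0.33 | 12 | 13.1% |
| 0.30 | 0.42 | 0.27 | 10 | 40.9% |

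At q = 0.05 the cut-off stays at 14 and the chance at 2.1%.

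**If such patients succeed half as often (k = 0.5)**

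The benchmark is 0.57, 0.54 or 0.51 for q = 0.10, 0.20 or 0.30, so its fall halves to 3, 6 or 9 points. The false-claim chance is 2.1, 5.8 or 13.1%.

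**Opposite direction**

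Suppose 10% of the comparator always fail, but another 20% are easier cases succeeding 0.30 more often (0.90), and the remaining 70% succeed at 0.60. The benchmark is 0.10 × 0 + 0.20 × 0.90 + 0.70 × 0.60 = 0.60. The two differences cancel exactly.

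**The case against.** The strongest reply is that no direction can be shown. The documents do not describe who is in the historical cohorts, so q may be zero and the bias with it. Inclusion requires active, sight-threatening disease with high-dose steroid in view, and admits patients still active on immunosuppression. These may be harder cases than the historical average, which would work against the pellet. This stands, and it settles that the net direction is unknown.

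A reader might infer that patients excluded for systemic disease were bound to fail the 7.5 mg endpoint. The documents do not support that. The exclusion names no dose, and section 3 treats chronic prednisone at or below 7.5 mg as suitable for long-term use, so some could succeed. Certain failure holds only for those kept above 7.5 mg, or on any oral dose for the discontinuation endpoint.

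A reader might also infer that the IOP and glaucoma exclusions tilt the comparison the same way. They have no stated link to the prednisone dose. Any effect on the comparison of IOP events again depends on who is in the comparator.

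The dose mechanism is confined to the secondary comparison in 7b. The primary outcome in 7a and the comparison in 7c state no dose condition. There, historical patients kept on systemic steroids could even have better ocular control and raise the benchmark. The unequal endpoints in 7b are a separate problem that would remain with identical populations.

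Finally, 7b refers to published data, so patient-level access is not promised. Section 7c does list the Johns Hopkins cohort and the SITE database apart from the published MUST data, which makes access plausible but not certain.

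None of this supplies the missing rule. Unknown cohort make-up is a reason to fix the comparator population in advance, and the rule is worth having whichever way the bias runs.

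**Conclusion.** The concern holds in a limited form. Section 7 leaves the comparator population undefined, and following it as written can give a biased non-inferiority comparison in 7b. Steroid-requiring systemic disease is one conditional route by which that bias would favour the pellet. The documents do not support saying that the comparison is known to favour it.

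The size depends wholly on assumptions. It runs from nothing (no such patients in the comparator) to an 18-point drop in the benchmark and a false-claim chance of 40.9% instead of 2.1% (30% of the comparator, all failing, p = 0.60, margin 0.15, one-sided 0.025). It should be corrected before the historical rates are drawn.

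**What to change.** In 7b and 7c, state the following.

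- Where patient-level records are available (assumed for Johns Hopkins, and for SITE if accessible), historical rates come from patients who meet all section 5 criteria that the records can identify. These include adult age, active sight-threatening intermediate or posterior uveitis with high-dose steroid considered, and no systemic disease requiring systemic corticosteroids. The severity criterion must be applied along with the exclusions, because filtering on the exclusions alone could bias against the pellet.
- List the criteria that the records cannot identify. Uncontrolled IOP and advanced glaucoma may be among them, since section 5 gives no thresholds.
- Report rates by prior immunosuppression (already on treatment or newly started), which the section 4a baseline visit records.
- Elsewhere, use the closest published subgroup and say how it differs from section 5.
- Label any unrestricted comparison descriptive, and accompany it with a sensitivity analysis over q as above.

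The cost is wording, the work of a filtered extract, and a smaller comparator sample with a wider interval. No patient visit or procedure changes.

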3. **Background:** Intermediate and posterior uveitis are thought to be severe intraocular inflammation that may lead to permanent visual loss. It is estimated that these forms of uveitis comprise the fifth or sixth leading cause of blindness and tend to affect working class age patients, thus causing loss of work hours and diminished productivity and quality of life. Because the posterior segment of the eve is not adequately treated by corticosteroid drops often systemic drug therapy is used including oral corticosteroids or prednisone. Prednisone can have a myriad of side effects in approximately onequarter to one-third of cases treated in tertiary care centers such as ours, additional medications such as immunosuppressive drugs are required to control the disease and/or to allow for appropriate tapering of oral prednisone to subsequent levels that have a low side effect profile when delivered over a long period of time. Typically, chronic prednisone therapy in doses of 7.5 mg daily or less are thought to have a low enough side effect profile to be amenable to long-term therapy. However frequently immunosuppressive drugs are required to get the dosing to this level. There are occasions when patients are intolerant of any dose of oral corticosteroids or are intolerant of the higher doses of oral corticosteroids (30 - 60 mg daily) and therefore this treatment modality is avoided due to prednisone's attendant side effects. Although periocular and intravitreal corticosteroids injections may be performed, with these modalities the standard of care is to wait until the disease reactivates before instituting such therapy and therefore a chronic suppressive dose is not obtained. fluocinolone acetonide implant (Retisert®, Bausch and Lomb, Tampa, FL) is FDA-approved for the treatment of intermediate and posterior uveitis and it is equally effective in controlling uveitis as highdose oral corticosteroids but avoids the systemic side effects associated with the use of high doses of oral corticosteroids. However, this form of local therapy has high rates of ocular side effects, including ocular hypertension causing glaucoma and/or requiring glaucoma surgery and cataracts. Furthermore, every two and half to three years the implant is exhausted of corticosteroid and therefore repeat surgical insertion of another implant may be required. A useful potential therapy for the treatment of these patients would be a shorter-acting local corticosteroid that could be delivered in conjunction with systemic immunosuppressive drug therapy that would have a lower ocular side effect profile but still would be effective enough to replace the use of high-dose systemic corticosteroids in the treatment of active intermediate or posterior uveitis. It is possible that the dexamethasone pellet could fill this unique role in the treatment of uveitis. We propose this proof of concept study to evaluate dexamethasone pellet for this specific use among patients with active intermediate and posterior uveitis.

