The fluocinolone acetonide implant is FDA-approved for the treatment of intermediate and posterior uveitis and it is equally effective in controlling uveitis as high-dose oral corticosteroids but avoids the systemic side effects associated with the use of high doses of oral corticosteroids. However, this form of local therapy has high rates of ocular side effects, including ocular hypertension causing glaucoma and/or requiring glaucoma surgery and cataracts. Furthermore, every two and half to three years the implant is exhausted of corticosteroid and therefore repeat surgical insertion of another implant may be required. A useful potential therapy for the treatment of these patients would be a shorter-acting local corticosteroid that could be delivered in conjunction with systemic immunosuppressive drug therapy that would have a lower ocular side effect profile but still would be effective enough to replace the use of high-dose systemic corticosteroids in the treatment of active intermediate and posterior uveitis. It is possible that the dexamethasone pellet could fill this unique role in the treatment of uveitis. We propose this proof of concept study to evaluate the dexamethasone pellet for this specific use among patients with active intermediate and posterior uveitis.

b. Justification and safety information if FDA approved drugs will be administered for non-FDA approved indications or if doses or routes of administration or participant populations are changed.

- N/A
- c. Justification and safety information if non-FDA approved drugs without an IND will be administered.
- N/A. The dexamethasone pellet is FDA-approved for the treatment of intermediate and posterior uveitis.

7. Study Statistics

- a. Primary outcome variable.
 - Control of uveitis at the 1 month, 2 month, 3 month, 6 month and 12 month time points. Cumulative incidences of uveitis control will be compared to historical data from the Johns Hopkins cohort and from the Systemic Immunosuppressive Treatment of Eye Diseases (SITE) Research Group.
- b. Secondary outcome variables.

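### Does section 7 leave it unclear whether the result compared with history is control ever reached or control present at the visit?

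*Combined protocol and SAP*

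**What the plan says.** The combined protocol and SAP describes the efficacy result in three places.

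- **Section 7a (primary outcome).** The first sentence gives the times: "Control of uveitis at the 1 month, 2 month, 3 month, 6 month and 12 month time points". The next gives the measure used against history: "Cumulative incidences of uveitis control will be compared to historical data from the Johns Hopkins cohort", with a second historical source added.
- **Section 7b (secondary outcomes).** This states what counts as controlled inflammation (vitreous cells, anterior chamber cells, chorioretinal lesions). It takes the cumulative incidence of that control at months 3 and 6 and compares it with published figures "of the cumulative incidence of steroid-sparing success" and of stopping oral steroid. The non-inferiority goal appears here and nowhere else. Side effects are compared "via rates and cumulative incidences at 12 months".
- **Section 7c (statistical plan).** After the sample size of 20, it says "data regarding success of control of uveitis at the 6 and 12 month examinations will be compared with historical published data". The cumulative term is absent.

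Section 4b allows repeat pellets at months 3, 6 and 9 and every three months afterwards. Section 4a also allows other treatment by medical judgment from month 6. Section 4f, on treatment failure, is marked not applicable. No section defines cumulative incidence or says how later activity, or control after a repeat pellet, is counted.

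**The concern.** In ordinary use, a cumulative incidence of control at month 12 is the share of patients who have reached control at some time up to month 12. A patient controlled at month 2 and active at month 12 stays a success. The first sentence of 7a and the wording of 7c can instead be read as status at the examination, where that patient is a failure.

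Loss of control is plausible here. The Background says that the usual practice with periocular and intravitreal steroid is to "wait until the disease reactivates before instituting such therapy and therefore a chronic suppressive dose is not obtained". Section 6a describes the treatment sought as a "shorter-acting local corticosteroid that could be delivered in conjunction with systemic immunosuppressive drug therapy", and repeat pellets are foreseen.

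Two things could go wrong. A cumulative figure might be read as control at month 12. Or visit-level control from this study might be set against published data that 7b describes only as cumulative incidences. With two candidate measures and no written counting rule, one might also fear that the measure could be chosen after the results are known.

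**Working it through.** **What the documents supply.** They give n = 20 (7c), the time points 1, 2, 3, 6 and 12 months (7a) and the definition of control (7b). They give no rate of gaining control, no relapse rate and no historical rate. There is therefore no stated figure to reproduce, and the rates below are assumptions.

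**Step 1: the passages side by side.**

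| Place | Times | Measure named |
|---|---|---|
| 7a, first sentence | 1, 2, 3, 6, 12 months | control (type not named) |
| 7a, second sentence | those just listed | cumulative incidence |
| 7b, pellet | 3, 6 months | cumulative incidence |
| 7b, published data | not given | cumulative incidence |
| 7b, side effects | 12 months | rates and cumulative incidences |
| 7c | 6, 12 months | success of control (type not named) |

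Wherever the type of measure for control is named, it is cumulative.

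**Step 2: size per patient.** 1/20 = 5 percentage points. Clopper-Pearson 95% intervals are 68.3 to 98.8% for 18/20 (90%) and 62.1 to 96.8% for 17/20 (85%). They overlap from 68.3 to 96.8%.

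**Step 3: how far the measures could part.** Use a monthly two-state chain in which all patients start active. Let g be the monthly chance of gaining control and r the monthly chance of losing it. Without repeat pellets:

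- controlled at month t: c(t) = g/(g + r) × [1 − (1 − g − r)^t]
- ever seen controlled by month 3: E3 = 1 − (1 − g)³
- by month 6: E6 = 1 − (1 − E3)(1 − c(3))
- by month 12: E12 = 1 − (1 − E6)(1 − c(6))

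The last two lines hold because patients not yet seen as controlled are active at the last visit and so start the chain afresh.

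Example with g = 0.3, r = 0.15:

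- c(3) = 0.6667 × (1 − 0.55³) = 0.556; c(6) = 0.648; c(12) = 0.666
- E3 = 1 − 0.7³ = 0.657
- E6 = 1 − 0.343 × 0.444 = 0.848
- E12 = 1 − 0.152 × 0.352 = 0.946
- Gaps: 10.1 points (month 3), 19.9 (month 6), 28.0 (month 12)

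Gap in points, range over g = 0.3, 0.4, 0.5:

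| Monthly relapse r | Month 3 | Month 6 | Month 12 |
|---|---|---|---|
| 0 | 0 | 0 | 0 |
| 0.01 | 0.7–1.0 | 1.6–1.7 | 1.9–2.7 |
| 0.02 | 1.4–2.0 | 3.2–3.3 | 3.8–5.3 |
| 0.05 | 3.5–4.9 | 7.7–8.0 | 8.9–12.1 |
| 0.10 | 6.9–9.5 | 14.3–14.8 | 16.2–21.1 |
| 0.15 | 10.1–13.9 | 19.9–20.6 | 22.3–28.0 |

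If relapse falls from 5–15% to 1–2% a month after month 6, the month 12 gap is 2.0 to 6.7 points. Suppose instead that every patient active at months 3, 6 or 9 has a repeat pellet, then gains control at an assumed 80% a month with no relapse for three months. Over the same relapse range the gap is then 0 to 17 points at month 6 and 0 to 21 at month 12. A 20-point gap at month 12 without repeat pellets needs about 9 to 13% monthly relapse sustained all year.

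**Step 4: is the relapse rule really open?** For a first-event cumulative incidence, later relapse and regained control change nothing. For a visit proportion, status on the day decides. Either measure fixes the rule. What neither settles is whether control reached for the first time after a repeat pellet or other treatment is a success. For the visit measure the same question arises for control present after such treatment.

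**The case for a change.** The strongest case for a change is that 7c is the plan's only statistical section and does not repeat the cumulative term. With a stated non-inferiority goal, the type of measure should be written down, and doing so would cost a sentence or two. Activity is already examined at every follow-up visit, so no new data would be needed. It is true that the term is undefined, that 7c is loosely worded, and that no section covers control after a repeat pellet.

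The rest carries less weight. The non-inferiority goal sits in 7b, where the measure is named for both sides; 7c sets no test. The relapse argument is thin. The Background sentence describes injections given alone after reactivation, whereas here the pellet serves "to control the uveitis whilst immunosuppressive drugs are being instituted or adjusted". The phrase in 6a contrasts the treatment sought with an implant lasting two and a half to three years. Neither gives a relapse rate within 12 months. For a treatment meant to bring disease under control during that period, reaching control is a legitimate target. Visit proportions can be tabulated from the planned examinations at 7a's times without amending anything.

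One caution stands. Sharing a cumulative scale does not make 7b's comparison like for like, because control of inflammation is a different event from steroid-sparing success or stopping oral steroid. That is a separate matter, and choosing between cumulative and visit-level control would not resolve it.

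**Conclusion.** The concern identifies missing detail rather than an error in the planned analysis. Two of the three subsections name the cumulative measure, the third is compatible with it, and the treatment of relapse follows from the measure. An analyst would report the cumulative incidence against history, tabulate status at the visits from the same records, label each for what it is, and say how control after a repeat pellet or other treatment was handled.

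The certain part of the size is 5 points for each patient who reached control but is active at the visit. The rest is assumption: 0 to 28 points at month 12 over monthly relapse of 0 to 15% without repeat pellets, and about one patient or less if relapse is 1 to 2% a month. The true size is unknown and may be zero. In a single-arm proof of concept study of 20 patients, with no bias shown for the cumulative comparison on this ground, no change to the plan is called for.

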
4. Study Procedures

a. Study design, including the sequence and timing of study procedures
 (Distinguish research procedures from those that are part of routine care): Single arm proof of concept interventional study.

Specifics of each clinical visit including data collected and procedures performed are as follows:

- Baseline examination data collection consists of:
 - o Signed informed consent obtained
 - O Demographic data (age, gender, race, duration of uveitis, anatomic location of uveitis, smoking status, presence of systemic disease associated with uveitis)
 - Treatment history (current therapies for the treatment of uveitis, history of corticosteroid use including periocular corticosteroids, history of immunosuppressive drug use, need for IOP-lowering medications)
 - Past ocular history (any complications due to uveitis, any ocular surgeries or procedures, presence of amblyopia, history of glaucoma or ocular hypertension, treatment to lower intraocular pressure including laser procedures and/or surgeries
 - Ophthalmic examination including best-corrected visual acuity, IOP measurement, presence and degree of uveitis activity, presence of ocular complications including cystoid macular edema (CME), findings of slit lamp examination including presence and degree of cataract, findings of fundoscopic examination including cup to disc ratio.
 - Visual field assessment
 - O Slit lamp photos to assess cataract if eye(s) are phakic O Optic nerve photos
 - Results of baseline OCT and fluorescein angiography testing if clinically indicated NEI
 VFQ and EuroQol administered
- Dexamethasone pellet placement occurs within 14 days of baseline examination; for patients with bilaterally active uveitis, placement of a dexamethasone pellet in the second eye should occur within 14 days of the first implantation or within 30 day of the baseline examination.
 - O Adverse events related to the procedure will be collected (e.g., vitreous hemorrhage, elevated IOP, retinal detachment) at time of placement
- 1-month examination o Interval treatment history (current therapies for the treatment of uveitis, history of corticosteroid use including periocular corticosteroids, history of immunosuppressive drug use, need for IOP-lowering medications)
 - o Interval ocular history (any complications due to uveitis, any ocular surgeries or procedures, history of glaucoma or ocular hypertension, treatment to lower intraocular pressure including laser procedures and/or surgeries

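### The historical comparison specifies no weighting for immunosuppressive drug or uveitis location, so a difference in patient mix could mimic or mask a pellet effect

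*Combined protocol and SAP*

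**What the plan says.** Section 4a describes a "Single arm proof of concept interventional study", and section 4e confirms that there is no placebo or untreated arm. The comparison is therefore wholly external:

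- Section 7a, primary outcome, at months 1, 2, 3, 6 and 12: "Cumulative incidences of uveitis control will be compared to historical data from the Johns Hopkins cohort" and from SITE.
- Section 7b, months 3 and 6: control is set against published figures "of the cumulative incidence of steroid-sparing success (prednisone <=7.5 mg daily and controlled disease") and for stopping oral steroid, with non-inferiority as the goal. Ocular and systemic side effects are compared with those of oral prednisone at 12 months.
- Section 7c, months 6 and 12: "20 patients will be enrolled" and compared with published history. "Comparative data from the Johns Hopkins cohort, SITE database, and published MUST data will be utilized".

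The inclusion criteria in section 5 admit "Active sight-threatening intermediate or posterior uveitis for which immunosuppressive drug therapy is planned". Patients already on such a drug are also eligible if high-dose corticosteroid is indicated. No drug is named and no location split is set.

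Location is on the section 4a baseline list: "Demographic data (age, gender, race, duration of uveitis, anatomic location of uveitis" and further items. That list also has current uveitis therapies and past immunosuppressive use. A drug that is planned but not yet started is not listed as an item of its own. No analysis in section 7 uses location or drug.

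**The concern.** Without a concurrent arm, whatever separates the trial patients from the historical ones goes into the estimated pellet effect. Two such features are left free.

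The first is the background drug. Section 3 explains that immunosuppressive drugs serve to control the disease or to let prednisone be tapered. The section 7b benchmark combines controlled disease with a low prednisone dose, so it should depend in part on which drugs the historical patients received. If trial patients receive drugs with higher or lower success, the benchmark no longer describes what they would have done without the pellet.

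The second is location. The section 7b definition of control requires a limit on vitreous cells together with "trace or less anterior chamber cells; and inactive chorioretinal lesions". An eye that never had chorioretinal lesions has nothing to fail on the last component, so the definition may work differently in intermediate and posterior disease. This is plausible, but the documents do not show it.

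Limiting the comparator to eligible patients and aligning the start of follow-up would not remove the problem, since eligible patients can still differ in drug and location. What is at stake is the non-inferiority statement: a favourable mix could produce it without a useful pellet, and an unfavourable mix could deny it to a good one.

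**Working it through.** **Inputs from the documents.** n = 20, single arm (sections 4a and 7c). Historical control rates, stratum rates, stratum shares, non-inferiority margin, alpha and power are not stated. The figure of 20 therefore cannot be reproduced, and every rate, share, margin and alpha below is an assumption.

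**Step 1: formula.** Let r be the historical control rate in a stratum, and let w(hist) and w(trial) be the stratum's share in each source.

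- Crude benchmark = sum of w(hist) × r.
- Standardised benchmark = sum of w(trial) × r.
- Mix shift = standardised minus crude. With two strata this is (difference in share) × (difference in rate).

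**Step 2: size over assumed ranges.** Rate differences are 10 to 30 points and share differences 10 to 40 points.

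- Smallest: 0.10 × 0.10 = 1 point, or 0.01 × 20 = 0.2 patients.
- Middle: 0.20 × 0.30 = 6 points, or 1.2 patients.
- Largest: 0.30 × 0.40 = 12 points, or 2.4 patients.

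The sign depends on which source has more of the easier stratum.

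Example: stratum rates are 30% and 60%, and the better stratum has a 30% share in history and 70% in the trial.

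- Crude: 0.70 × 0.30 + 0.30 × 0.60 = 39%.
- Standardised: 0.30 × 0.30 + 0.70 × 0.60 = 51%.

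**Step 3: effect on a conclusion.** Assume a crude benchmark of 50% treated as fixed, one-sided alpha 0.025, and the exact binomial with n = 20. The superiority rule is then at least 15 of 20. With an assumed margin of 20 points, the non-inferiority rule is at least 11 of 20, because P(X ≥ 11 | 0.30) = 1.7%. With mix shift s, the true trial rate is 0.50 + s if the pellet equals the comparator, and 0.30 + s if it is 20 points worse.

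| Mix shift | Superiority declared, pellet equal | Non-inferiority declared, pellet 20 points worse | Non-inferiority declared, pellet equal |
|---|---|---|---|
| −12 | 0.1% | under 0.1% | 9% |
| −6 | 0.5% | 0.3% | 22% |
| 0 | 2.1% | 1.7% | 41% |
| +6 | 6.6% | 6.5% | 63% |
| +12 | 16.7% | 17.0% | 81% |

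**Step 4: against sampling error.** At 10 of 20 the exact 95% interval is 27% to 73%, about 23 points each way. The largest assumed shift is about half of that (12/23).

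**The case against.** The strongest case on the other side has five parts.

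- **Silence is not a choice.** A reader might infer that the plan has decided on one pooled figure per source. The documents do not say so. They refer to historical, published and comparative data, and drug- or location-specific figures are not ruled out. This stands: the finding is that nothing is specified.
- **The drug may matter little early.** By the inclusion criteria, high-dose corticosteroid is meant to control the eye while the immunosuppressive drug is started or adjusted. Drug mix may therefore count for less at months 1 to 3, which are three of the five primary time points. This stands, and the drug concern weighs more at months 6 and 12.
- **The location argument is thin.** A reader might infer that one location is simply easier to control. All patients enter with active disease and control requires every component, so a component met automatically does not by itself make control easier. No document gives rates by location. This stands as a limit.
- **Weighting could bring its own bias.** If the stratum were a drug chosen after the pellet, a switch prompted by a poor response would change the weights. This stands, and the fix excludes it.
- **Twenty patients cannot support strata, and this is only a proof of concept.** The part about tiny cells largely fails: the trial patients supply only the weights, and the stratum rates come from the historical cohorts. It is true that sampling error would often exceed the mix shift. But a confidence interval shows sampling error only and gives no sign that its reference value is misplaced. It is also fair that sources available only as published totals may offer no stratum rates.

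**Conclusion.** The omission is certain. The comparison is external, drug and location mix are free, and sections 7a to 7c specify no weighting, matching or stratum-specific comparator. A mix difference could mimic or mask a pellet effect.

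The size is not known. The 1 to 12 points either way follow from the assumed differences in rates and shares. The error rates in the table rest further on an assumed 50% benchmark, 20-point margin and alpha. A reader might take 12 points, or a false-positive risk near 17%, as the expected distortion. The documents support neither, and they do not show that the trial's mix will differ from history at all.

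This is a worthwhile and inexpensive improvement to the comparison. It does not show that the comparison would give a wrong answer.

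**What to change.** In sections 7a to 7c:

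1. Report two benchmarks side by side: the crude figure, and one standardised to the trial's own distribution of uveitis location. Where the comparator data allow, add coarse class of the immunosuppressive drug in use or planned at enrolment.
2. Fix the drug class at enrolment and never use a drug chosen after the pellet. Since the baseline list does not name the planned drug as an item, add it to the baseline form.
3. Take stratum-specific rates from the Johns Hopkins and SITE data. Merge sparse strata by a stated order, drug class first.
4. Base the non-inferiority statement on the standardised figure where it is available. Where a source offers only overall figures, as published MUST may, say so and label that comparison unstandardised.
5. For systemic side effects in section 7b, where data allow, take as comparator patients on prednisone plus an immunosuppressive drug, because trial patients have that background in place or planned.

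The cost is extra tabulation of comparator data, one baseline item and some added wording in section 7. No treatment or visit changes. Some comparator strata may be sparse, and confounding by severity and prior treatment will remain, which the report should state.
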